[figure not shown]
Pre-registration for quantitative part of Art on Prescription

[figure not shown]

Athens March, 10, 2024

Design

Stratified randomised controlled trial with two arms: arts intervention (any of the arts interventions, see list), which the investigators call here Active Group (AG) vs waitlist control (WL). Stratifying will happen at each site.

REMEMBER the investigators want to measure AG and WL, then WL becomes AG after 3 months and both the initial AG and the WL \rightarrow AG will be measured in exactly the same way for another 3 months.

AG for 3 months. Then goes into 3 month follow up.

WL for 3 months. Then this group receives intervention and becomes AG and has measurements for 3 months as the AG did.

There will be a 2-month break between T3 and T4 due to summer vacation

In the beginning, an open invitation to institutions of culture and mental health had been sent. Culture institutions i.e. Opera House, Contemporary Art Museum, National Theater etc. presented their action plans for interventional courses. Investigators did the connection between mental health and culture institutions.

Potential participants declared their preference for the interventional course such as dance, cinema etc. and they listed while an external investigator did the blind randomization into AG or WL group.

Measurement

Participants in both the AG and the WL groups will be measured on the following outcomes. Primary Outcome: Wellbeing Questionnaire (WEMWBS), PHQ-9, GAD-7 Secondary Outcomes: UCLA-20.

Frequency of Measurement:

→ The primary outcome will be measured at time points (for adults):

- T0: (before the randomisation; patient's personal data and demographics)
- T1: (before the start of the intervention for the active group or the entry into the study for the WL group)
- T2: 6 weeks (after the start of the intervention for the active group or the entry into the study for the WL group)
- T3: 12 weeks (after the start of the intervention for the active group or the entry into the study for the WL group)

The secondary outcomes will be measured at time points 0 (T4) and 12 weeks (T5) for both AG and WL.

→The primary outcome will be measured at time points (for children/adolescents):

- T0: (before the randomisation; patient's personal data and demographics)
- T1: (before the start of the intervention for the active group or the entry into the study for the WL group)

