- T3: 12 weeks (after the start of the intervention for the active group or the entry into the study for the WL group)

The secondary outcomes will be measured at time points 0 (T4) and 12 weeks (T5) for both AG and WL.

Model

The investigators will follow standard practice for RCTs and apply an ANCOVA model to estimate the effects of treatment. The formalism is:

y ~ b0 + b1xtreatment_group + b2xtime + b3xtreatment_groupxtime + covariates (1)

Where, y is each outcome, b1-b3 are the regression coefficients and covariates denote covariates at randomisation (DETERMINE)

The inference of interest for the model concerns b3, the interaction term, as the investigators posit that there will be a difference in slopes between the treatment groups.

The inference is going to happen via an estimation of the t-statistic, defined as follows"

t = b3/SE(2)

Where SE is the standard error for coefficient b3

[figure not shown]
t > 1.96(3)

And 1.96 is the critical value for statistical significance at alpha = 0.05.

Target Sample Size per Arm

Parameters:

- power = 0.8
- alpha = 0.05
- Correlation between time points = 0.6 (a conservative estimate based on https://www.ncbi.nlm.nih.gov/pmc/articles/PMC2222612/)
- Effect size corresponding to d = 0.5

library(tidyverse) # for data wrangling library(faux) # for simulation

library(broom) # for tidy analysis results

set.seed(1974)

I will simulate the following

```

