# two groups, treatment and WL control.
# they start off with distributions with the same mean and sd (due to randomisation)
# the WL control stays the same, the treatment group changes to arrive at a d = 0.4, which i
# what investigators stipulated in advance
# the shape of the change should not matter that much for this linear model calculation

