# c) number of people, sample size, which I will vary for the simulation
# here comes the actual function
ancova sim func <- function(df means, sd across, n subjects, number sims,
correlations across){
 arts on pres sim <- sim design(
  n = n_subjects, # this is the per arm n
  between = list(group = c("active", "wl")),
  within = list(time = c("T1", "T2", "T3", "T4")),
  mu= df means.
  sd = sd across,
  dv = "score",
  r = correlations across,
  long = TRUE,
  plot = FALSE,
  rep = number sims
 )
 temp results <- lst()
 temp results disp <- lst()
 temp_p_values <- 0
 for(i in 1:n sims){
  temp_results[[i]] <- aov(score~ time + group + time*group , data =
arts on pres sim$data[[i]])
  temp_results_disp[[i]] <-broom::tidy(temp_results[[i]])</pre>
  temp_p_values[i] <- temp_results_disp[[i]]$p.value[3]
 return(temp_p_values)
}
```

```

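### Equation (1) models time as one straight line while the sample-size code models separate visits; the line gives the adult week-6 score no weight with complete data and can bias the week-12 effect if adults are lost after week 6 and the effect is not linear

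*Protocol*

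**What the plan says.** The Model section of the protocol writes "y ~ b0 + b1xtreatment_group + b2xtime + b3xtreatment_groupxtime + covariates (1", with one coefficient for time and one for group by time. Inference is on b3, because "the investigators posit that there will be a difference in slopes between the treatment groups". The test is t = b3/SE, and the section states that "1.96 is the critical value for statistical significance at alpha = 0.05". This is a 1-df straight-line model.

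Under Frequency of Measurement, adults give primary outcomes at T1, at "T2: 6 weeks (after the start of the intervention" and at "T3: 12 weeks (after the start of the intervention". Children and adolescents have T1 and T3 only.

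Under Target Sample Size per Arm, the simulation fits "aov(score~ time + group + time*group , data" on data in which time has the levels T1 to T4, and takes the third p-value, which is the time-by-group row. The treated means are equally spaced and the control means flat. A comment says "the shape of the change should not matter that much for this linear model calculation". The section states no rate of loss to follow-up and prints no resulting sample size.

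**The concern.** Two parts of one document describe different tests: a difference in slopes (1 df) in the equation, and a joint test over visits (3 df) in the code. The power curve therefore does not describe the declared analysis.

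The straight line also has its own consequence for adults. It fixes the week-6 effect at half the week-12 effect. With complete data the week-6 score then adds nothing to b3. For an adult seen only to week 6, the week-6 change is projected forward to week 12 as if it would double. If an arts course acts early and holds, acts early and fades, or acts late, that projection is wrong, and b3 no longer measures the 12-week effect even when loss is random and equal between arms.

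**Working it through.** **Inputs.** From the protocol's simulation settings: SD 10.4 at every visit and d = 0.5, so the full effect is 0.5 x 10.4 = 5.2 WEMWBS points (taken here as a size, without sign). Correlation 0.6 is from the parameter list; the code sets 0.5. Adult visits are at weeks 0, 6 and 12. Assumed, because the document does not give them: a fraction f lost at random after T2, equal in both arms, and a model with exchangeable correlation within person.

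**1. Weights with complete data.** The centred times are -6, 0 and +6. The slope is the sum of (t - 6)y divided by the sum of (t - 6)², that is (-6 y1 + 0 y2 + 6 y3)/72. Multiplying by 12 gives y3 - y1, so the weights on (T1, T2, T3) are (-1, 0, +1). Generalised least squares (GLS) gives the same weights under exchangeable and AR(1) correlation with equal variances. The variance per participant is 2(1 - 0.6) = 0.8 in units of SD², the same as for the T3 - T1 change.

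The zero is not general. If variances rise in the ratio 1 : 1.2 : 1.4, the T2 weight is 0.11 even with complete data.

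**2. Weights with loss.** At f = 0.2 the GLS weights are (-0.914, 0.016, 0.946) for completers and (-0.140, 0.093) on T1 and T2 for those who leave. For a between-arm difference of 0 at T1, e6 at T2 and e12 at T3, the expected value of 12 x b3 is

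(0.016 + 0.093) x e6 + 0.946 x e12.

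- Plateau (5.2, 5.2): 0.109 x 5.2 + 0.946 x 5.2 = 5.48 (unrounded weights), against 5.2: +5%.
- Fading (5.2, 2.6): 0.109 x 5.2 + 0.946 x 2.6 = 3.02 (unrounded), against 2.6: +16%.
- Late (0, 5.2): 0.946 x 5.2 = 4.92, against 5.2: -5%.
- Linear (2.6, 5.2): 5.2, no bias.

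| Loss after T2 | Plateau (true 5.2) | Fading (true 2.6) | Late (true 5.2) |
|---|---|---|---|
| 0% | 5.2 | 2.6 | 5.2 |
| 10% | 5.33 | 2.79 | 5.07 |
| 20% | 5.48 | 3.02 | 4.92 |
| 30% | 5.67 | 3.30 | 4.73 |

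A model with visit indicators and the same covariance returns the true week-12 value in every cell. At 20% loss the plateau bias is 4.0% under plain least squares and 7.7% to 10.2% under AR(1) correlation of 0.6 to 0.9, so its presence does not hang on one covariance.

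**3. Precision.** Variances of the week-12 effect (units of SD², r = 0.6), line against visits:

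| Loss | Line | Visits | SE increase with visits |
|---|---|---|---|
| 0% | 0.800 | 0.800 | 0% |
| 10% | 0.860 | 0.861 | 0.1% |
| 20% | 0.930 | 0.9375 | 0.4% |
| 30% | 1.015 | 1.036 | 1.0% |
| 40% | 1.118 | 1.167 | 2.1% |
| 50% | 1.248 | 1.350 | 4.0% |

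With variances rising 1 : 1.2 : 1.4 the increase is 0.4% with complete data and about 3% at 30% loss.

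**4. The shape comment.** The code's 3-df test responds to S, the sum over the four visits of (e - mean e)², with e the effect as a fraction of its final size.

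| Path over T1 to T4 | S | Power at 160 per arm, r = 0.5, no loss |
|---|---|---|
| 0, 1/3, 2/3, 1 (linear, as in the code) | 0.56 | about 84% |
| 0, 1, 1, 1 | 0.75 | about 96% |
| 0, 0, 0, 1 | 0.75 | about 95% to 96% |
| 0, 0, 1, 1 | 1.00 | over 99% |

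The final d is 0.5 in every row. The figure of 160 per arm is the first point on the code's grid at which a re-run passes 80%; it is not a number printed in the document.

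**The case against.** A 1-df linear contrast is a legitimate choice, and a difference in slopes is what the plan says it wants. The bias needs two conditions together: loss after week 6 and an effect that is not linear. The plan's own path is linear, so under its own assumption the bias is zero, and with equal random loss it is also zero when there is no effect, which leaves the type I error intact. For a plateau at 20% loss the shift is 5.48 - 5.2 = 0.28 points. With 160 per arm the SE is 10.4 x sqrt(2 x 0.93/160) = 1.12 points, so the shift is about a quarter of an SE. No loss rate is stated, and nothing in the document suggests a fading effect. Covariance and missing-data handling may also sit in an analysis plan that is not shown. All of this stands and limits the size of the point.

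A reader might go further and infer four things that the documents do not support.

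- That the week-12 effect is biased as the plan stands. This needs both conditions above.
- That the straight line can never save more than 1% of the SE. The saving reaches 2% to 4% at 40% to 50% loss.
- That the week-6 score is always discarded, or counts double for those who leave. Zero weight is exact only with complete data and equal variances. The doubling describes a leaver's own slope; leavers' week-6 scores carry only about 0.09 of the weight in b3 at 20% loss.
- That the problem is the same however T1 is used. The section calls the model an ANCOVA. If T1 is a covariate and only T2 and T3 are outcomes, time has two values, linear and visit coding coincide, and this argument does not apply.

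The shape comment can be defended as referring to a complete-data simulation. It still fails there, because the test that the simulation runs depends on shape.

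**Conclusion.** The point holds in limited form. The firm part is internal: equation (1) is a 1-df straight line, the sample-size code tests a 3-df interaction over visits, and the two must be reconciled. The comment on shape is wrong for the code's own test, with power running from about 84% to over 99% at the same final effect.

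The part on bias is conditional. With T1 to T3 as outcomes and equal variances, 12 x b3 equals the difference in 12-week change when nobody is lost. With loss after week 6 and a non-linear effect it is off by about 5% (plateau or late) or 16% (fading) at 20% loss. The loss rate, the shapes and the exchangeable correlation of 0.6 are assumptions of this check. The point concerns adults only, since children have no week-6 visit. It is worth acting on because the remedy is cheap, not because the bias is shown to be large.

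**What to change.** In equation (1), replace the linear time term with visit indicators: y ~ group + T2 + T3 + group x T2 + group x T3 + covariates, with visits linked within participant and children contributing T1 and T3 only. Name group x T3 as the coefficient tested in place of b3, and report group x T2 as the 6-week effect in adults. Change the sample-size code to test that same 1-df contrast on the scheduled visits, and delete the comment on shape.

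The cost is wording and a re-run of the simulation, with no new data or participants. Under equal variances the week-12 estimate and its SE are unchanged with complete data. Under exchangeable correlation the SE rises by 0.1% to 1% at 10% to 30% loss and by 2% to 4% at 40% to 50% loss, and by somewhat more if variances rise over time.

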# to create equally spaced value, my idealised decline of values
the treatment means <- seg(mean T1, mean T4, length.out = 4)

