# }
# sum(temp p values<0.05)/length(temp p values)
# create a function for all the above -----
# I will simulate the following
# two groups, treatment and WL control.
# they start off with distributions with the same mean and sd (due to randomisation)
```

- # the WL control stays the same, the treatment group changes to arrive at a d = 0.4, which i
- # what investigators stipulated in advance
- # the shape of the change should not matter that much for this linear model calculation
- # what should matter are
- # a) sds which I will keep the same as in baseline
- # b) number of measurements, stipulated to be n = 4
- # c) number of people, sample size, which I will vary for the simulation

Brief description of tools:

- Patient's personal data and demographics (i.e. name, age, nationality, religion, educational level, marital status, socio-economic characteristics, medical history, mental health problems, medication, therapies).
- The Warwick-Edinburgh Mental Wellbeing Scale (WEMWBS). This tool was developed in order to measure mental wellbeing in the general population by Tennant et al. (2007). It consists of 14 items responding using a 5-point Likert scale from 1 (never) to 5 (all the time). The overall score is calculated by summing the responses for every item without reversing none. The minimum overall score ranges from 14 to 70. Higher scores indicate increased mental wellbeing. The scale has been widely used nationally and internationally for monitoring, evaluating projects and programmes and investigating the determinants of mental wellbeing. An efficient internal consistency was proven using Cronbach's alpha score which was 0.89 for the student sample and 0.91 for the general population sample. Also, test-retest reliability at one week was high (0.83). The Greek validation showed acceptable internal consistency (Cronbach's alpha score 0.90).

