The Generalised Anxiety Disorder Assessment (GAD-7) is provided to screen symptom severity for the four most common anxiety disorders (generalized anxiety disorder, panic disorder, social phobia and posttraumatic stress disorder). GAD-7 constructed by Spitzer et al (2006) and validated in Greek by Vogazianos et al (2022). It consists of 7 items. The GAD-7 score is computed by assigning scores of 0, 1, 2, and 3, to the response categories of 'not at all', 'several days', 'more than half the days', and 'nearly every day', respectively, and summing together the scores for the seven questions (scores range from 0 to 21). Higher levels indicate increased anxiety. There are cut-offs for severity of anxiety as: (i) score 0-4: Minimal Anxiety; (ii) score 5-9: Mild Anxiety; (iii) score 10-14: Moderate Anxiety; (iv) score greater than 15: Severe Anxiety. The internal consistency of the GAD-7 was excellent (Cronbach α = 0.92) and testretest reliability was also efficient (intraclass correlation = 0.83) (Spitzer et al., 2006). [Spitzer RL, Kroenke K, Williams JB, et al; A brief measure for assessing generalized anxiety disorder: the GAD-7. Arch Intern Med. 2006 May 22;166(10):1092-7]. [Vogazianos P, Motrico E, Domínguez-Salas S, Christoforou A, Hadjigeorgiou E. Validation of the generalized anxiety disorder screener (GAD-7) in Cypriot pregnant

and postpartum women. BMC Pregnancy Childbirth. 2022 Nov 15;22(1):841. doi: 10.1186/s12884-022-05127-7].

• The Patient Health Questionnaire-9 (PHQ-9) is a questionnaire which measures depression and grade severity of symptoms in general medical and mental health settings using nine DSM-5 criteria for major depression within the last two weeks. PHQ-9 constructed by Kroenke et al. (2001) and validated in Greek by Hyphantis et al. (2011) is using a four-point Likert-type scale. After summing all responses (0=not at all, 3=nearly every day), scores range from 0 to 27, with higher levels indicating increased symptom severity (0–4 no to minimal; 5–9 mild; 10–14 moderate; 15–19 moderately severe; 20–27 severe). The internal reliability of the PHQ-9 was excellent, with a Cronbach's α of 0.89 in the PHQ Primary Care Study (Kroenke et al., 2001) and 0.82 in Greek validation (Hyphantis et al., 2011).

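### As printed, equation (3) declares significance only for t above +1.96, so under any single arm coding it cannot detect benefit on at least one of the three primary outcomes; it should read |t| > 1.96.

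*Protocol*

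**What the plan says.** The Measurement section names three primary outcomes: "Primary Outcome: Wellbeing Questionnaire (WEMWBS), PHQ-9, GAD-7". The Model section applies one regression to all of them: "Where, y is each outcome, b1-b3 are the regression coefficients". Interest lies in b3, the group-by-time interaction, "as the investigators posit that there will be a difference in slopes between the treatment groups".

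Equation (2) sets t = b3/SE, which keeps its sign. Equation (3) is printed as t > 1.96, followed by "And 1.96 is the critical value for statistical significance at alpha = 0.05". The section gives no absolute value, no statement of sidedness, no arm coding and no reverse-scoring of any outcome.

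The section describing the tools gives the scale directions:
- WEMWBS: "The minimum overall score ranges from 14 to 70. Higher scores indicate increased mental wellbeing"
- PHQ-9: "scores range from 0 to 27, with higher levels indicating increased symptom severity"
- GAD-7: "summing together the scores for the seven questions (scores range from 0 to 21). Higher levels indicate increased anxiety"

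The code under Target Sample Size per Arm counts p-values below 0.05 from the time-by-group F test. That test takes no account of sign.

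**The concern.** A rule that looks only at the upper tail works for every outcome only if benefit moves every outcome the same way. Here it does not. Applied literally, equation (3) would report a real benefit as non-significant on at least one primary outcome, and the arm coding would decide which one. The document is a pre-registration, meant to fix the decision rule before the data are seen, so the printed rule should agree with the alpha, the hypothesis and the test used for sample size. As printed it agrees with none of the three.

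**Working it through.** **Inputs.** From the Model section: t = b3/SE, the rule t > 1.96, alpha = 0.05. From Target Sample Size per Arm: power 0.8; in the code d = -0.5, mean 43.5, SD 10.4, four occasions, correlation 0.5 (0.6 in the parameter list). Scale directions come from the tool descriptions. The protocol states no sample size, so any N below is illustrative.

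**Step 1: the stated alpha.** The two-sided 5% critical value is 1.95996 and the one-sided 5% value is 1.645.
- P(|Z| > 1.96) = 2 × 0.0250 = 0.0500, which reproduces the protocol's figure.
- P(Z > 1.96) = 0.0250, which does not.

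So the sentence that ties 1.96 to alpha = 0.05 is right for a two-sided test, and the inequality printed above it is not that test.

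**Step 2: the sign of b3 under benefit.**

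| Outcome | Better is | b3 if active = 1 | b3 if waitlist = 1 |
|---|---|---|---|
| WEMWBS | higher | positive | negative |
| PHQ-9 | lower | negative | positive |
| GAD-7 | lower | negative | positive |

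Neither coding makes b3 positive for benefit in all three rows. Recoding outcome by outcome would do so, but the protocol states no such rule.

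**Step 3: what this does to power.** Assume the non-centrality that gives 80% two-sided power: 1.960 + 0.842 = 2.802.
- b3 positive: P(t > 1.96) = P(Z > 1.960 - 2.802) = P(Z > -0.842) = 0.80.
- b3 negative: P(t > 1.96) = P(Z > 1.960 + 2.802) = P(Z > 4.762) = 9.6e-7, about 0.000001.
- |t| > 1.96: 0.80 for either sign.

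**Step 4: the protocol's own scenario.** With d = -0.5, four occasions and an illustrative 100 per arm, 1,500 simulated trials were analysed by ordinary least squares with linear time.

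| Rule | r = 0.5 | r = 0.6 |
|---|---|---|
| t > 1.96, active = 1 | 0% | 0% |
| t > 1.96, waitlist = 1 | 83% | 85% |
| abs(t) > 1.96, either coding | 83% | 85% |

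The printed rule gives nothing or full power depending on a coding that the protocol does not state. With the absolute value, coding no longer matters.

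**Step 5: the direction in the code.** A mean of 43.5 lies outside the ranges of PHQ-9 (maximum 27) and GAD-7 (maximum 21), so among the primaries it can only be WEMWBS. The code moves the active arm to 43.5 - 0.5 × 10.4 = 38.3, in its words "to create equally spaced value, my idealised decline of values". On WEMWBS that is a worsening. Because the F test ignores sign, changing d to +0.5 changes no power figure.

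**The case against.** The best reply is that everything around equation (3) is two-sided. The value 1.96 belongs to a two-sided 5% test, the hypothesis is a difference in slopes without direction, and the simulation uses a test blind to sign. A figure is also missing from the extracted text directly above equation (3), so absolute-value bars may have been lost in reading the PDF. If so, the plan has no error here. All of this stands as evidence of intent, and it is why the original must be checked first. It does not make the inequality correct if the PDF prints it the same way.

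A reader might also infer more than the documents support:
- **That a one-sided test is planned, or that the trial will miss a benefit on depression or anxiety.** That would require an analyst to follow the inequality and ignore the stated alpha and hypothesis.
- **That the 0% result in the protocol's scenario is general.** It holds only with the active group coded 1. The code lists the active group first, and R's default treatment contrasts would then code the waitlist as 1. The final analysis coding is not stated.
- **That the rule is faulty because it can call harm significant.** So can |t| > 1.96; this is not specific to the defect.
- **That the negative d shows a directional intent or spoils the sample size.** The F test is invariant to sign, so it shows neither.
- **That missing arm coding is a defect in itself.** Coding may be left to an analysis plan, and under a two-sided rule it does not affect significance.

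**Conclusion.** The point holds for the rule as printed. Under any single arm coding, t > 1.96 cannot detect benefit on at least one primary outcome: PHQ-9 and GAD-7 if the active group is 1, WEMWBS if the waitlist is 1. Its size is half the stated alpha, and it conflicts with the non-directional hypothesis and with the F test in the sample-size code. The sign argument needs no sample size; only the illustrative probabilities rest on the assumed non-centrality of about 2.8. The conclusion assumes that the original PDF shows no absolute-value bars and that outcomes are not recoded one by one. The likely cause is a slip in notation, so the point is a correction to the text and not evidence that the trial is underpowered or that a directional test was meant.

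**What to change.** Check equation (3) in the original PDF. If it has no absolute-value bars, write it as |t| > 1.96 and state that the test is two-sided at alpha = 0.05. Then read the sign of b3 against the scale directions already given in the tool descriptions, stating the arm coding wherever b3 is reported. This costs one line, keeps the 1.96 threshold, and leaves the simulated power as it is because the simulation already uses a non-directional test. Correcting the sign of d in the WEMWBS code is optional tidying.
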